## 10. PATIENT WITHDRAWAL FROM STUDY PARTICIPATION

Patients may withdraw from the study at any time at their own request, or they may be withdrawn at any time at the discretion of the Investigator or Sponsor for safety, behavioral, or administrative reasons.

If a patient does not return for a scheduled visit, every effort should be made to contact him/her. In any circumstance, every effort should be made to document patient outcome, if possible. The Investigator should inquire about the reason for withdrawal, requests the patient to return for a final visit, if applicable, and follow-up with the patient regarding any unresolved adverse events.

If the patient withdraws from the study and also withdraws consent for disclosure of future information, no further evaluations should be performed and no additional data should be collected. The Sponsor may retain and continue to use any data collected before such withdrawal of consent.

Patients may continue with therapy with the study medication unless any of the following occurs:

- Disease progression or relapse at any time;  
Note: If patient is clinically stable and has observation of blasts reduction or suspected disease stabilization in the judgment of the investigator the patient may continue with dosing after an adverse event taking into account dose modification in section 9.2.3;  
Note: Patient must *discontinue treatment for failure to achieve at least partial response after 9 cycles*
- Global deterioration of health status requiring discontinuation;
- First-cycle DLT, unless the patient is demonstrating clinical benefit and can continue the treatment at a reduced dose, as agreed by the Investigator and Sponsor;
- CCI with systemic and/or bulbar impairment
- Unacceptable study drug-related toxicities incompatible with continuation of treatment with NMS-03592088 according to the judgment of the Investigator, even at a reduced dose;
- Change in the patient's medical status (including pregnancy) such that the Investigator believes that patient safety may be compromised or that it would be in the best patient's interest to stop treatment;
- Treatment delay for >14 days due to treatment related non-hematologic toxicity unless the patient is demonstrating clinical benefit as agreed by the Investigator and Sponsor;
- The patient becomes eligible for hemopoietic stem cell transplantation (HSCT)
- Substantial deviation from specified inclusion or exclusion criteria or non-compliance by the patient with protocol requirements;

- Investigator's decision;
- Patient's refusal to continue study treatment;
- Patient lost to follow up;
- Death;
- Study terminated by Sponsor.

Patient will be withdrawn from the study in case of:

- Withdrawal of consent;
- Patient lost to follow up;
- Death;
- Study terminated by Sponsor.

Data to be collected for the end of study treatment/withdrawal are described in the Schedule of Events, reported in Section 1.

Patients will be followed for at least 28 days after the last dose of study drug for adverse events and for 18 months from patient's first study drug dose for survival status.

## 11. ASSESSMENTS

### 11.1. Timing of Assessments

Schedule of Events, reported in Section 1, summarizes information on the timing of assessments to be performed during Phase I and Phase II portions of the study. Protocol waivers or exemptions are not allowed.

Procedures conducted as part of the participant's routine clinical management (e.g., bone marrow aspirate or biopsy) and obtained before signing of the Informed Consent Form may be utilized for screening or baseline purposes provided the procedures met the protocol-specified criteria and were performed within the time frame defined in the Schedule of Events.

### 11.2. Disease Assessments

Peripheral blood and/or bone marrow aspirate/biopsy will be collected for cytogenetic molecular and phenotypic characterization of the disease at the study entrance, during treatment, as applicable, and at the end of treatment.

#### 11.2.1. Immunophenotyping, Cytogenetic and Molecular Characterization

CCI

For further details regarding antigens to be assessed by FACS, please refer to Study Manuals.

#### 11.2.2. Detection of FLT3-ITD or D835/I836 mutations

CCI

- At Investigator's discretion

Throughout the clinical study, bone marrow and/or blood samples collected at screening and at the end of treatment will be used also for centralized NGS analysis and biomarkers expression evaluation. For further details on these evaluations see Section 11.6.2 and the Study Manuals.

### 11.3.3. Clinical evaluation of Extramedullary Disease

For all patients, clinical evidence of extramedullary disease (EMD) will be collected, in the eCRF, in terms of presence/absence of the disease. The site of involvement will also be reported in the eCRF. During the study, the EMD status will be clinically evaluated at screening, during the physical examinations performed on treatment, at the same times of disease evaluation, at the end of treatment and at Investigator's discretion.

In the presence of EMD, lesions must be followed by imaging and/or other clinical evaluations, and the choice of methods is at the Investigator's discretion. For CMML patients, splenomegaly should always be assessed using CT or MRI scan (3-D ultrasound will be acceptable if other aforementioned scans are not available within the allotted timeframes of the intra-study evaluation).

### 11.3.4. Definition of the response

The response to treatment will be evaluated:

- For AML patients, following criteria as defined by the ELN recommendations [6, 7]. For reference, see Appendix 2;
- For CMML patients, following the International Working Group criteria [56]. For reference see Appendix 3, Appendix 4 and Appendix 5.

## 11.4. Outcomes Research Assessments

Not applicable.

## 11.5. Safety Assessments

Safety assessments include collection of AEs, SAEs, triplicate 12-lead ECGs, vital sign measurements, physical examinations and safety laboratory tests. These will be performed periodically at baseline, during treatment and at End of Treatment (and/or at Investigators' discretion).

Assessment of adverse events will include type, incidence, severity (graded by the National Cancer Institute [NCI] Common Terminology Criteria for Adverse Events [CTCAE], Version 5.0), timing, seriousness, and relatedness.

Baseline signs and symptoms will be recorded at baseline and then reported as adverse events during the trial if they worsen in severity or increase in frequency.

## 11.5.1. Adverse Event Assessment

### 11.5.1.1. Definition of Adverse Events

#### 11.5.1.1.1. Adverse Event

According to ICH definition and EU directive (2001/20/EC), an AE is defined as any untoward medical occurrence in a patient or a clinical trial patient administered a medicinal product and which does not necessarily have to have a causal relationship with the use of the product. An adverse event can therefore be any unfavorable and unintended sign (e.g. an abnormal laboratory finding), symptom, or diagnosis temporally associated with the use of a medicinal product, whether or not considered related to the medicinal product.

Any untoward medical occurrence, which occurs outside the period of patient follow-up defined in the protocol, is not considered an AE. Symptoms or medically significant laboratory or instrumental (e.g., by electrocardiography) abnormalities of a pre-existing condition should not be considered an AE. However, occurrence of new symptoms, laboratory or instrumental abnormalities, as well as worsening of pre-existing ones, is considered AEs.

#### 11.5.1.1.2. Serious Adverse Events

A serious adverse event (SAE) is an adverse event that falls into one or more of the following categories:

- Results in death;
- Is life-threatening, i.e., an event which, in the view of the Investigator, placed the patient at risk of death at the time of event (it does not include an event which hypothetically might have caused death if it were more severe);
- Requires inpatient hospitalization or prolongation of existing hospitalization;
- Results in persistent or significant disability/incapacity, where disability is defined as a substantial disruption of a person's ability to conduct normal life functions, either reported or defined as per clinical judgment;
- Is a congenital anomaly/birth defect (if exposure to product just before conception or during pregnancy resulted in an adverse outcome in the child);
- Is any other important medical event, i.e., may not result in death, be life-threatening, or require hospitalization, but based upon appropriate medical judgment, it may jeopardize the patient and may require medical or surgical intervention to prevent one of the outcomes listed in the points above. Examples of such events include allergic bronchospasm requiring intensive treatment in an emergency room or at home, and blood dyscrasias or convulsions that do not result in inpatient hospitalization.

A non-serious adverse event is any adverse event that does not meet the criteria listed above or the outcome cannot be determined with the information provided.

Each adverse event has to be classified by the Investigator as serious or non-serious.

In this study the following do not have to be classified as SAEs:

- Admission to hospital required by the protocol;
- Hospitalization for routine treatment or monitoring of the studied indication not associated with any deterioration in patient's clinical condition;
- Hospitalization or prolongation of hospitalization for technical, practical, or social reasons, in absence of an AE;
- A procedure requiring hospitalization planned prior to starting the study treatment; must be documented in the Source Documents and the e-Case Report Form (e-CRF). Prolonged hospitalization for a complication remains a reportable SAE;
- Hospitalization for an elective treatment of a pre-existing condition unrelated to the studied indication;
- Events definitely related to disease progression.

However, all Adverse Events with outcome deaths occurring during the reporting period have to be reported as SAEs, even if due to disease progression.

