### 11.5.1.5. Adverse Event Follow Up after the End of the Reporting Period

The following events should be followed after the end of the reporting period (i.e., 28 days after the last study treatment administration):

1. SAEs with outcome ‘not recovered’ or ‘unknown’ at the end of the reporting period.
2. Non-serious events classified as related to the investigational study treatment with outcome ‘not recovered’ or ‘unknown’ at the end of the reporting period.

These events should be followed until they resolve or until the Investigator determines, whenever possible, that they have become “chronic” or “stable”. Resolution of such events is to be documented on the SAE Form and/or on eCRF.

In addition, if after the end of the reporting period, suspected serious adverse reactions or deaths are reported to the Investigator and he/she believes that they are related to the IMP, it is the Investigator’s responsibility to report these suspected serious adverse reactions to the Sponsor. Such suspected serious adverse reactions will be reported using a Serious Adverse Event Report or by any other way chosen by the Investigator.

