#### 11.5.1.7. Reporting Requirements

Each adverse event has to be classified by the Investigator as SERIOUS or NON-SERIOUS (as per paragraph 11.5.1.1.2). This classification of the event determines the reporting procedures to be followed. If a serious adverse event occurs, reporting will follow local and international regulations, as appropriate.

If a serious adverse event occurs the Sponsor Pharmacovigilance has to be notified within 24 hours of awareness of the event by the Investigator, by e-mail (here below Pharmacovigilance address/contacts). Further detailed reporting procedures are described in the Study Manual.

PPD

The initial report should be followed by submission of more detailed adverse event information as soon as it is available. Additional follow-up should be provided up to the resolution of the SAE, the Investigator determines it has become chronic or stable (not recovered) or a new anticancer therapy is initiated.

Reporting requirements for adverse events are summarized in the following table.

REPORTING REQUIREMENTS FOR ADVERSE EVENTS		
Seriousness	Reporting Time	Type of Report
SERIOUS	Within 24 hours	Initial report on designated SAE form
	As soon as available	Follow-up/Final report on designated SAE form
NON-SERIOUS	As per eCRF procedure	Appropriate section of eCRF

Suspected Unexpected Serious Adverse Reactions (SUSARs) will be reported by Sponsor or designee to all competent Regulatory Authorities, to the Ethics Committees and to all the Investigators involved, according to local regulations and requirements stated in ICH Good Clinical Practice.

In the rare event that the Investigator does not become aware of the occurrence of a serious adverse event immediately (for example, if an outpatient trial patient initially seeks treatment elsewhere), the Investigator has to report the event within 24 hours after learning of it and document his/her first awareness of the adverse event.

Serious adverse events should also be consistently recorded in the appropriate section of eCRF.

Non-serious adverse events have to be reported in the appropriate section of eCRFs only excluding Adverse Events of Special Interest (see section 11.5.1.1.3).

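### The definition of a non-serious adverse event lets missing information default an unclear event to non-serious, which can delay or miss its 24-hour report

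*Protocol*

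**What the plan says.** Protocol section 11.5.1.1.2 opens with the positive definition: "A serious adverse event (SAE) is an adverse event that falls into one or more of the following categories". After the list of criteria it describes a non-serious event as "any adverse event that does not meet the criteria listed above or the outcome cannot be determined with the information provided". It then asks for a two-way decision with no pending category: "Each adverse event has to be classified by the Investigator as serious or non-serious".

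Section 11.5.1.7 attaches the reporting route to that decision: "This classification of the event determines the reporting procedures to be followed". For the serious branch, "If a serious adverse event occurs the Sponsor Pharmacovigilance has to be notified within 24 hours of awareness of the event by the Investigator". The non-serious branch goes to the eCRF only, except for adverse events of special interest (AESIs).

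Section 11.5.1.5 lists what is followed after the reporting period. The first item is SAEs that have not recovered or whose outcome is unknown. The second begins "Non-serious events classified as related to the investigational study treatment with outcome" and covers the same two outcome states. Unrelated non-serious events are not on the list.

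SAP section 9.8.1 reports serious AEs separately from other AEs. Its visible text has no rule for an event whose seriousness is undetermined.

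**The concern.** When information is incomplete, a seriousness definition should say which way to lean. This one leans towards non-serious, and that label is the switch between a report within 24 hours and an eCRF entry. Treatment is home-based, the drug is in its first-in-human study, and section 12.5 foresees no independent data monitoring committee. Safety oversight rests on reviews between the sponsor and the investigators, and drug-related SAEs are one of their inputs. Prompt notification of possibly serious events therefore matters here. The events exposed to the clause are the poorly documented ones, for which an early alert would prompt someone to obtain the missing facts.

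**Working it through.** No arithmetic applies: the documents state no rate of undetermined outcomes. The check sets the passages side by side and follows each kind of event through them.

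**Step 1: what the clause adds.** The definition has two limbs joined by *or*: no criterion met, or outcome not determinable. The first limb already makes every event that fails all criteria non-serious. The second limb therefore matters only for events that would not otherwise be non-serious, or for which that is not yet known.

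**Step 2: what outcome means.** The word can mean resolution status, as in 11.5.1.5, or the seriousness outcomes such as death or disability. Section 11.5.1.9 gives the second reading some support, because it ties seriousness to outcome or action criteria. On the first reading the clause conflicts with 11.5.1.5, which keeps an SAE of unknown outcome as an SAE. On the second, it says that an event that cannot be matched to a criterion for lack of information is non-serious. Either way, missing information leads to non-serious.

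**Step 3: follow each kind of event through the rules.**

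| Event | Class under 11.5.1.1.2 | 24-hour report |
|---|---|---|
| Plainly meets a criterion (for example a known admission), outcome unknown | Serious by the opening sentence, non-serious by the clause; 11.5.1.5 treats such events as SAEs | Kept, if the opening sentence governs |
| Known fatal outcome in the reporting period | SAE by a separate sentence of 11.5.1.1.2 | Kept |
| Confirmed AESI | Either | Kept (11.5.1.1.3, 11.5.1.7) |
| May meet a criterion, but facts too thin to tell | Opening sentence not yet triggered; the clause gives non-serious | Late or missed |

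The fourth row carries the finding. It can include a suspected neuromuscular event, because 11.5.1.1.3 makes AESI reporting depend on a confirmed diagnosis after neurological evaluation. No visible passage tells the investigator to handle a fourth-row event as serious until clarified.

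**Step 4: follow the fourth row downstream.**

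- *Notification:* late if the event is reclassified when facts arrive, missed if it is not.
- *SAP outputs:* the SAP places final analyses after the database is cleaned and locked (closing text of section 5.2). The event is missing from the serious-AE outputs only if it is still labelled non-serious at that point.
- *Follow-up after the reporting period:* lost only if the event is still non-serious and judged unrelated. A related non-serious event that is unresolved or of unknown outcome stays on the list.

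**The case against.** The best defence is that the clause should be read with the rest of the section. The opening sentence is the operative definition, and several criteria do not wait for a final outcome. Risk of death is judged by the investigator when the event happens, an admission is a fact once it occurs, and the important-medical-event category rests on medical judgement. Section 11.5.1.5 shows that the protocol expects SAEs with unknown outcome. This stands for events that visibly meet a criterion. For events that cannot yet be judged, the clause remains the only visible instruction, and it points the wrong way.

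A reader might infer that every event with an undetermined outcome becomes non-serious and loses its 24-hour report. The documents do not support that: the first three rows of the table keep the report.

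A reader might also see a contradiction with 11.5.1.7, which says "The initial report should be followed by submission of more detailed adverse event information as soon as it is available". That sentence governs what follows an initial SAE report, not how an unclear event is first classed. The example in the same section, "if an outpatient trial patient initially seeks treatment elsewhere", belongs to a safeguard: the investigator must report within 24 hours of learning of the event. It shows that late information is foreseen, but it is not itself a source of harm. It applies to events recognised as serious, so it does not rescue the unclear ones.

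Two further points for the defence stand. The visible Phase II safety monitoring counts grade 4 non-hematological events, prolonged grade 4 neutropenia leading to withdrawal and drug-related deaths, and the sponsor-investigator calls also review grade 3-4 events. Neither depends wholly on the serious label. Section 11.5.1.7 also refers to more detailed reporting procedures in the Study Manual, which is not available here and may contain a better rule.

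**Conclusion.** The concern holds in a limited form. The clause makes missing information a default to non-serious, conflicts with the opening of its own section and with 11.5.1.5, and can delay or lose the 24-hour report of an event that may be serious but cannot yet be classified. Loss from the SAP's serious-AE outputs, or from follow-up after the reporting period, needs the further conditions given in step 4.

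The size cannot be derived. A reader might take the study maximum of approximately 180 patients as the exposure. That figure is the ceiling for both parts of the study, including Phase I, and says nothing about how many events would be unclear or how many a future edit would reach.

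The conclusion assumes that investigators follow the clause as written and that no rule outside the visible documents overrides it. The severity is moderate: worth correcting, but not a defect that must be fixed before the trial can proceed.

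**What to change.** In protocol section 11.5.1.1.2, delete the limb of the non-serious definition about an outcome that cannot be determined. Nothing is lost, because an event that meets no criterion is already non-serious without it.

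In the same place, state that an event that may meet a seriousness criterion but cannot yet be classified is reported as serious within 24 hours and downgraded if later information allows. Check that sections 11.5.1.5 and 11.5.1.7, and the Study Manual, say the same.

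The cost is a sentence or two at the next amendment and a few initial SAE reports that are later downgraded. No dosing rule, eligibility criterion or analysis changes.

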#### *11.5.1.1.3. Adverse Events of Special Interest*

Adverse events of special interest (AESI) are defined as events (serious or non-serious) which are of scientific and medical concern specific to the Sponsor's product or program, for which ongoing monitoring and rapid communication by the Investigator to the Sponsor may be appropriate. Such events may require further investigation in order to characterize and understand them.

During the dose escalation part of the study neurological adverse events involving the neuromuscular transmission (CCI ) have been reported with NMS-03592088 (See section 9.2.7.1). External ocular movements deficit with ptosis and diplopia were the typical pattern.

The occurrence of any sign and/or symptom suggestive of a CCI , such as:

- a) ptosis, diplopia, weakness, muscular weakness (after exertion), dysphagia, dysphonia, dyspnea
- b) fatigue, asthenia, hyposthenia, hypoactivity, if associated with any of the above

should prompt the evaluation by a neurologist and, if the diagnosis of CCI is confirmed, the event should be reported as AESI.

All AESIs [diagnosis and specific sign(s)/symptom(s)] have to be reported within 24 hours according to the procedures described for serious adverse event in section 11.5.1.7.

### 11.5.1.2. Unexpected Adverse Event

An unexpected AE is one, the nature or severity of which is not consistent with the applicable product information that, for the present CT, is the Investigator Brochure (IB) [55].

### 11.5.1.3. Eliciting Adverse Event Information

The Investigator has to report all directly observed AEs and all AEs spontaneously reported by the trial patient using concise medical terminology. In addition, each trial patient will be questioned about adverse events at each clinic visit following signature of the Informed Consent Form. The question asked will be “Since your last clinical visit have you had any health problems?”

